# 1. STUDY SYNOPSIS

| Title of clinical trial                          | Transplant ureteric stent removal: Early
versus standard removal. A Randomised
controlled trial.   |
|--|--|
| Short Name                                       | TrUST ( Transplant Ureteric Stent Trial )   |
| Sponsor name                                     | Guy's and St Thomas' NHS Foundation Trust  |
| Medical condition or disease under investigation | Renal Transplantation  |
| Purpose of clinical trial                        | To determine if early transplant ureteric stent
removal (eTUSr) leads to a decrease in stent
related complications, specifically urinary
infection, haematuria, pain and migration.   |
| Primary objective                                | To determine the effect of early transplant
ureteric stent removal (eTUSr) on stent
related complication rates   |
| Secondary objective(s)                           | 

To determine the effects of early TUS removal by new method on:

1. ureteric complication rates

2. patient acceptability

3. procedural costs

4. resource availability and allocation

  |
| Study Design                                     | Randomised controlled trial  |
| Study End-points                                 | 
 
Stent complications monitored at each
OPA for 3 months
 
Ureteric leak monitored at each OPA for
3 months
 
Ureteric stenosis monitored at each OPA
for 6 months
 
Patient acceptability –QOL questionnaires
at 1 & 6 weeks
 
Economic evaluation – diary card on day
of stent removal, evaluation of hospital
costs at 6 months
 
                       |
| Sample Size                                      | 176 Renal Transplant Patients  |
| Summary of eligibility criteria                  | 
 
Patients undergoing renal transplantation
 
Children aged 2 years and above
 
Adults
 
   |
| Summary of exclusion criteria                    | 
 
Urinary Tract exclusion: urinary
diversion; pelvi-ureteric junction
obstruction; surgical concern regarding
the vascularity of the transplant ureter;
donor kidney stone; early use of mTOR
inhibitors
 
Increased risk of bleeding: post operative
systemic heparinisation; >3 cycles of pre-
operative plasma exchange (DFFP);
kidney capsule removed at retrieval
 
 |

| Г  |  |
|--|--|
|  | 3. Simultaneous Kidney and Pancreas
Transplant (SPK)  |
| Investigational medicinal product and dosage             | N/A; this is not a trial of an investigational medical product   |
| Active comparator product(s)                             | N/A  |
| Route(s) of administration                               | N/A  |
| Maximum duration of treatment of a subject               | N/A  |
| Procedures: Screening & enrolment                        | All patients undergoing kidney
transplantation will be considered for
enrolment  |
| Baseline   | Baseline recipient data will be recorded.  |
| Treatment period
End of Study                         | The intervention is non-pharmacological.
Patients will be randomised to one of two
groups: control (conventional cystoscopic
TUS removal) or trial (new method with early
TUS removal), refer to flow diagram. Trial
group will have their TUS attached to their
catheter during surgery. Both Catheter and
TUS will be removed on day 5 post surgery.
The control arm will undergo catheter
removal on day 5 and the current
conventional method of cystoscopic TUS
removal at week 6.
Follow-up visits and tests are part of the
transplantation protocol in the centres. Data
will be obtained from the medical notes and
local centre databases for up to 1 year
Patients will be followed-up for 1 year |
| Procedures for safety monitoring                         | Complications will be reported to the Data   |
| during trial   | Safety Monitoring Committee (DMC). The   |
|  | committee will meet in the $1^{st}$ month & then at 3 monthly intervals.   |
| Criteria for withdrawal of patients on
safety grounds | 
 
An increased rate of stent related
complications in the eTUSr arm (>20%)
 
An increase in ureteric complications in
the eTUSr arm (>1% urinary leak or >2
cases in the 1st month; 20% ureteric
stenosis or >3 cases at 3 months)
 
Clinically and statistically different
outcomes are shown in either arm and
continuation of the study is considered
unethical
 
  |
| Regulatory submissions on safety grounds                 | Not required as not a CTIMP  |

#### 2. STUDY FLOW CHART

# 3. BACKGROUND

During kidney transplantation a plastic tube (stent) is placed in the transplant ureter, between the renal pelvis and the bladder. Meta-analyses of randomised controlled trials on the use of transplant ureteric stents (TUS) have shown that routine use of a TUS reduces major post transplant urological complications, particularly urinary leaks and ureteric stenosis .

# The Current Problem:

However stent complications occur in around 20% of patients, both adults and children . Studies suggest that TUS complications; which include urine infection, stent migration and pain; are related to the time stents remain in-situ 

The optimum timing for stent removal is currently not known, however a recent study suggested that stents should be removed at 2 to 4 weeks post transplantation . In our centre we have reduced the time that our ureteric stents remain in-situ from 12 to 6 weeks post transplant on the basis of internal audit of transplant stent complications. Nevertheless, we continue to observe a 15-20% post transplant ureteric stent complication rate (internal unpublished audit); mainly of urinary infection and stent migration.

Most stent removal is performed under local anaesthesia by flexible cystoscopy, although a general anaesthetic cystoscopy is occasionally needed in adults and routinely in children. A novel technique of suturing the ureteric stent to the urethral catheter was described in 1998. This allowed the removal of both the stent and urethral catheter together without recourse to cystoscopy or anaesthesia. In this original description of the technique the urinary catheter/sutured ureteric stents were removed at a mean time of 8 days (range 6 to 10 days). A retrospective study of this technique in 590 patients showed it was safe and also reduced the urological complications seen without a stent . In this study the urinary catheter/sutured ureteric stents were removed at a mean time of 10 days (range 8 to 12 days). A visit to the Mayo Clinic transplant unit by members of our transplant team observed the routine use of the novel technique to remove both urinary catheter/sutured ureteric stenal transplant, but to our knowledge their practice has not been subjected to peer-review publication or prospective clinical trial.

# Potential Benefits:

To patients: No need for a cystoscopy for stent removal. Patients are keen to avoid a second procedure (cystoscopy) for stent removal, as shown by a questionnaire carried out in our centre. With no required cystoscopy, patients and their relatives should benefit from reduced travel costs, work related problems, loss of income and time. To patients and hospital: early stent removal with the new technique should decrease the

incidence of stent related problems, especially urinary tract infection. This may decrease need for antibiotics, risk of antibiotic resistance and hospital admissions.

To hospital: The cost of outpatient flexible cystoscopy under local anaesthetic is around  $\pounds$ 766 per patient. Costs when general anaesthetic is required are considerably higher. This method will potentially free-up flexible cystoscopy resources to improve access for other patients requiring urgent diagnostic cystoscopy for bladder cancer.

# Proposal:

A randomised controlled trial will compare the current standard TUS removal (sTUSr) to the novel technique with early TUS removal (eTUSr) at 5 days post transplantation. This will allow development of best clinical practice in this important area of early post kidney transplant care. A urinary catheter is routinely placed into the bladder at the start of kidney transplant surgery. The optimal timing of urethral catheter removal post renal transplant has also not been defined but day 5 after surgery is the standard universally accepted day for catheter removal after kidney transplant surgery. Our unit removes the urethral catheter on day 5 post renal transplant. We do not leave the urethral catheter in the patient routinely longer than 5 days as this would be associated with increase risk of urinary infection.

The main design issue relates to the fact that in the intervention arm (eTUSr) there are 2 changes from current practice - earlier stent removal (day 5 rather than 6 weeks after surgery) and removal of stent together with catheter (rather than with cystoscopy). We wish to test eTUSr that allows removal of the stent together with the catheter so that patients benefit from not needing a cystocopy. Potentially this will be a huge benefit to patients. We have therefore chosen to remove the stent together with the catheter (in the eTUSr arm) on day 5 after surgery.

Our centre performs 200 kidney transplants per year, including the largest number of children in the UK. As an Academic Health Science Centre we are well-positioned to conduct clinical research. We have support from the Trust Research and Development Service, the London (South) Comprehensive Local Research Network (CLRN) and the Guy's and St Thomas' Biomedical Research Centre (BRC). Other UK transplant centres are potential trial collaborators.

# 4. TRIAL OBJECTIVES

The study has 4 main objectives:

1) To determine if early transplant ureteric stent removal (eTUSr) leads to a decrease in stent related complications

2) To determine the effect of eTUSr on ureteric complication rates (ureteric leak or stenosis)

3) To determine if eTUSr results in better patient acceptability

4) To determine if eTUSr leads to improved cost effectiveness

# 5. TRIAL DESIGN

#### 5.1 Statement of Design

A randomised control trial evaluating the effect of early transplant ureteric stent removal to reduce stent related complications post renal transplant.

#### 5.2 Study Population

Trial centres will include:

- Guy's and St Thomas NHS Foundation Trust (GSTT)
- The Evelina Children's Hospital (GSTT)
- Great Ormond Street Hospital for Children NHS Trust (GOSH)
- King's College Hospital (KCH)
- Kent & Canterbury (K&C)

#### **Inclusion Criteria**

- Children (age 2-16) needing kidney transplant
- Adults needing kidney transplant (17 75yrs)

#### **Exclusion Criteria**

- Urinary Tract exclusion:
  - urinary diversion e.g. *ileal conduit, cutaneous ureterostomy, mitrofanoff; duplex transplant ureter*
  - donor kidney pelvi-ureteric junction obstruction
  - donor kidney cyst with calyceal connection (increased risk urinoma)
  - surgical concern regarding the vascularity of the transplant ureter
  - donor kidney stone and use of bench (ex-vivo) ureteroscopy
  - early use of mTOR inhibitors (early use is very uncommon as the drug has well documented concerns regarding worse tissue healing)
- Risk of bleeding:
  - kidney capsule removed at retrieval
  - need for post operative systemic heparinisation
  - >3 cycles of pre-operative plasma exchange (DFFP) as part of transplant desensitisation program
- Simultaneous Kidney and Pancreas Transplant (SPK)

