#### 5.4 Recruitment Process

Patients will be informed of the trial at pre-transplant education sessions so that they will be familiar with the study when they are formally invited to participate at the time of admission for kidney transplant surgery. They will be given patient information leaflets and the trial will be explained in concordance with Good Clinical Practice (GCP). All data will be held in concordance with GCP. Following informed written consent patients will be randomised into one of the 2 study arms.

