#### 5.5 Sample Size Determination

An audit over the last 3 years has demonstrated that between 15 to 20% of patients have TUS-related complications, mainly UTI in the first 3 months post transplant surgery. On this basis, we aim to reduce our TUS-related complication rate to a target rate of 5%. Statistical power calculations were performed by [name], Statistician, KCL, London. Based on a chi-squared test with 80% Power and a 5% 2-sided type I error rate 88 patients per group are required assuming a current 20% TUS-related complication rate. The corresponding number is 160 patients per group assuming a current 15% TUS-related complication rate.

As there is a degree of uncertainty in the starting TUS-related complication rate, we will perform a sample size re-estimation based on predictive power after 25 patients per group which we anticipate will be 3 months into the trial.

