# 5.9 Trial Treatments

The study is a randomised control trial in which there are two potential study arms to which patients are randomly allocated, see below. It is not possible to blind patients or investigators as to whether they will undergo the standard technique or the novel technique for stent removal due to noticeable differences in the method of procedure.

*Group 1*: CONTROL - Standard technique for TUS removal (sTUSr) *Group 2*: TRIAL - Novel technique with early TUS removal (eTUSr)

A TUS is placed at the time of surgery along with a urinary catheter in all patients. Patients in Group 1 will have the urinary catheter removed on the ward on the 5th post-operative day. They will then undergo a cystoscopy, under either local or general anaesthetic, at week 6 to remove the TUS. Cystoscopy and stent removal takes

approximately 10 minutes. Patients will be given a prophylactic intravenous injection of antibiotic to cover the procedure. Patients in Group 2 will have the TUS attached to the urinary catheter at the time of surgery. These patients will have the urinary catheter removed on the ward on the 5th post-operative day in the standard way. As the TUS is attached to the catheter it will be removed at the same time as removal of the catheter. Catheter removal simply involves deflating the catheter balloon to allow it to slide out from the bladder. It is a non-invasive procedure that does not cause discomfort or risk to the patient. Removing the catheter with the stent attached will not change this. Group 2 therefore do not require cystoscopy.

The study will be performed prospectively. Patients that require kidney transplantation will be recruited and allocated to a study arm. Participants of the study will have routine clinical follow up in the same way as non-participants. A diary card will be completed by both trial groups on the day of their stent removal. Stent related symptom assessment and quality of life questionnaires will be completed by all adult participants at week 1 and week 6. Data will be collected on all participants regarding ureteric complications, stent related complications, health economics and patient quality of life assessments for 3 months post transplantation. Complications of ureteric stenosis will monitored for up to 6 months post transplantation.

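### Randomisation is tied only to consent, so a subjective surgical exclusion and two that can arise after surgery may be applied by staff who already know the arm

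*Protocol*

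**What the plan says.** Protocol 5.4 (Recruitment Process) has patients "formally invited to participate at the time of admission for kidney transplant surgery". It continues: "Following informed written consent patients will be randomised into one of the 2 study arms". Section 5.6 describes the online system, the 1:1 ratio and stratification by age. Neither section ties allocation to inspection of the kidney and ureter or to a final eligibility check.

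Three of the exclusions in 5.2 matter here:
- "surgical concern regarding the vascularity of the transplant ureter", for which no objective threshold is given;
- "need for post operative systemic heparinisation";
- "early use of mTOR inhibitors", which the protocol describes as very uncommon.

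Section 5.9 fixes the latest time at which the arm must be known: "Patients in Group 2 will have the TUS attached to the urinary catheter at the time of surgery". Section 5.10 describes how the surgeon makes that attachment. On blinding, 5.9 says: "It is not possible to blind patients or investigators".

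**The concern.** An exclusion criterion protects a randomised comparison only if it is applied before allocation, or without knowledge of it. Here one criterion is a surgeon's opinion, and two can come into being after the operation. The person applying them may know the arm.

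The incentive is not symmetrical. A doubtful ureter loses its stent on day 5 in the eTUSr arm and at week 6 in the control arm, so there is more reason to voice concern in the first case. Section 8.2 names urinary leak as the main potential complication of early removal. The vascularity criterion therefore bears on the safety outcomes that the trial compares. If doubtful patients were removed more often from eTUSr, harm in that arm would be understated. The primary comparison could also shift in favour of eTUSr, to the extent that these patients also have more stent-related complications.

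**Working it through.** **Order of events.**

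| Step | Where | When |
|---|---|---|
| Invitation | 5.4 | at admission |
| Randomisation | 5.4 | after consent; moment not stated |
| Ureter vascularity judged | 5.2 | not stated; needs sight of the ureter, at the bench or in theatre |
| Arm must be known | 5.9, 5.10 | at stent placement |
| Unplanned heparinisation or mTOR use | 5.2 | can be after surgery |

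Wherever randomisation falls between consent and stent placement, the last row comes after it. Nothing puts the vascularity judgement before it.

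**The plan's own sample size.** Section 5.5 says: "Based on a chi-squared test with 80% Power and a 5% 2-sided type I error rate 88 patients per group are required", for 20% against 5%. The uncorrected chi-squared formula gives n = 75.12, rounded up to 76. With the continuity correction, n/4 × [1 + √(1 + 4/(n × 0.15))]² = 87.95, rounded up to 88. For 15% against 5% the same steps give 140.1, then 159.5, rounded up to 160. Both stated figures reproduce. The total of 176 is 2 × 88, so it holds no allowance for late exclusions.

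**Primary endpoint, assumed inputs.** Suppose no true effect, a 20% complication rate and 88 randomised per arm. A share f of patients is high-risk, with complication rate h. A fraction q of them is removed, from eTUSr only. The values of f, h and q are assumptions; the protocol gives none of them.

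- Rate in the other patients: r = (0.20 − f·h)/(1 − f)
- eTUSr rate after removal: [(1 − f)·r + f·(1 − q)·h]/(1 − f·q)

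| f | h | q | patients removed (88·f·q) | eTUSr rate | spurious difference | two-sided rejection probability |
|---|---|---|---|---|---|---|
| 5% | 40% | 0.5 | 2.2 | 19.5% | 0.5 points | 5.1% |
| 5% | 60% | 1 | 4.4 | 17.9% | 2.1 points | 6.4% |
| 10% | 60% | 1 | 8.8 | 15.6% | 4.4 points | 11.4% |

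First row as an example: r = (0.20 − 0.02)/0.95 = 0.1895; eTUSr rate = (0.18 + 0.01)/0.975 = 0.1949. The rejection probability is for an uncorrected chi-squared comparison at a nominal 5%. The planned difference is 20% − 5% = 15 points.

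**Leak.** Section 8.4 includes a leak rate above 1% in eTUSr among its stopping conditions. One leak in 88 is 1/88 = 1.14%, above the limit; none is 0%. Removing one patient who would have leaked can change the reading of that condition.

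As a further assumed example, let 5% of ureters cause concern and carry a 20% leak risk, with 1% in the rest. The full-arm rate is 0.95 × 1% + 0.05 × 20% = 1.95%. With all of them removed it is 1.0%. With half removed it is (0.95% + 0.5%)/0.975 = 1.49%. The leaks lost by removing all of them number 0.05 × 0.20 × 88 = 0.88, less than one expected event.

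**The case against.** A reader might infer that patients are randomised at admission. The protocol does not say so: they are invited then and randomised after consent, at an unstated interval. The flow chart in section 2 is not visible in the text available and might show the sequence. Randomisation in theatre would be compatible with 5.4. This stands, and it is why the point is that the order is not fixed, not that it is known to be wrong. It does not remove the problem: even allocation in theatre precedes an unplanned post-operative need for heparin or an mTOR inhibitor.

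A reader might also infer that patients who meet a criterion late are dropped from the analysis. No section says this. Section 7.2 asks that stent removal before or after day 5 be documented with its reason, which gives a worried clinician a route that needs no exclusion. The analysis set may be defined in a SAP that is not shown, and its absence from the protocol is not the complaint. The order of eligibility and allocation is protocol content, however. An analysis rule alone would not settle the status of a patient whom the protocol calls ineligible.

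Three further points stand. Vascularity may be assessable at the bench, as retrieval and bench findings elsewhere in 5.2 suggest. Heparinisation can be planned in advance. Leak and stenosis are not components of the primary composite in 7.1, so an effect on the primary endpoint needs these patients to have more infections, migration, pain, haematuria or fragmentation as well.

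**Conclusion.** The concern holds as a sequencing weakness. Followed as written, the plan permits exclusion after allocation by staff who know the arm, on one subjective criterion and two that can arise post-operatively. The documents do not show that unequal exclusion occurs, and they do not support saying that the randomised comparison is broken.

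The size is unknown. On the assumed inputs the primary endpoint shifts by about 0.5 to 4.4 points. The upper end needs a 10% high-risk share, a 60% complication rate and complete removal from one arm only. The safety reading is more fragile, because a single leak among 88 patients decides whether the 1% limit is passed. The direction, with more removals from eTUSr, is plausible from the day 5 against week 6 contrast but is not demonstrated. This should be corrected, and the stated sample size is not in dispute.

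**What to change.** - **5.4 and 5.6:** randomise through the existing online system only after the donor kidney and ureter have been inspected and eligibility has been recorded, just before the stent is placed.
- **5.2:** state that exclusion criteria are assessed on what is known or planned at that point. The criteria themselves, including those on heparinisation and mTOR inhibitors, stay as they are; only the time of assessment is fixed.
- **Late occurrences:** state that a randomised patient who later meets a criterion is managed at the clinicians' discretion, stays in follow-up, and stays in the primary analysis in the allocated arm. Report the number of such patients by arm.

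The cost is protocol wording and a short randomisation step in theatre. The sample size remains 88 per group.

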# 5.3 Number of Subjects

We estimate a sample size of 176 patients will need to be recruited

#### 5.4 Recruitment Process

Patients will be informed of the trial at pre-transplant education sessions so that they will be familiar with the study when they are formally invited to participate at the time of admission for kidney transplant surgery. They will be given patient information leaflets and the trial will be explained in concordance with Good Clinical Practice (GCP). All data will be held in concordance with GCP. Following informed written consent patients will be randomised into one of the 2 study arms.

#### 5.5 Sample Size Determination

An audit over the last 3 years has demonstrated that between 15 to 20% of patients have TUS-related complications, mainly UTI in the first 3 months post transplant surgery. On this basis, we aim to reduce our TUS-related complication rate to a target rate of 5%. Statistical power calculations were performed by [name], Statistician, KCL, London. Based on a chi-squared test with 80% Power and a 5% 2-sided type I error rate 88 patients per group are required assuming a current 20% TUS-related complication rate. The corresponding number is 160 patients per group assuming a current 15% TUS-related complication rate.

As there is a degree of uncertainty in the starting TUS-related complication rate, we will perform a sample size re-estimation based on predictive power after 25 patients per group which we anticipate will be 3 months into the trial.

